10.1 Primary Endpoint Definition

The primary objective of this study is to describe the expected real-world usage duration of Levosert for its different indications.

Duration of Levosert usage is defined as the difference in time between removal (with or without replacement) and insertion of the device. In the absence of detailed patient-level data and in the context of this survey, expected duration of Levosert usage for each indication will be calculated as follows:

Expected usage duration of Levosert (years)

$$= \sum_{i=1}^{6} (i \ x \ likelihood \ of \ Levosert \ removal \ in \ Year \ i)$$

+ (likelihood of Levosert removal beyond Year 6 x total expected usage duration in those patients)

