10.2 Determination of Sample Size

A convenience sampling approach was chosen aiming to reach a sufficiently large group of eligible HCPs who have collectively treated a substantial number of patients with Levosert for the HMB indication.

Based on the size and composition of the physician panel in the four study countries, it is estimated that a sample of approximately 380 HCPs would qualify to complete the questionnaire. Assuming an estimated 27,500 Levosert removals (from product launch until 2020) by approximately 11,200 OB-GYNs across the study countries (average 2.46 Levosert removals per OB-GYN), a sample of approximately 380 HCPs would achieve collective experience with the removal of approximately 820 Levosert IUS. Assuming an approximately balanced distribution by both indications – i.e., contraception only vs. HMB with and without intended contraception: 45% and 55%, respectively (Römer et al., 2009) –, this sample would cover approximately 450 Levosert removals in patients with HMB. Coverage of such a level of collective experience is deemed sufficient to generate a robust estimate on the expected duration of Levosert usage.

See Appendix 1 for detailed data supporting this convenience sampling approach.

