Appendix 1: Supporting Data for HCP Sample Size Determination

A feasibility assessment was conducted to understand the estimated number of Levosert removals since product launch in each country, the total number of practicing OB-GYNs, and the expected number of OB-GYNs that could be recruited from a large physician panel across the study countries (i.e., OB-GYNs who would be eligible and willing to participate).

The number of Levosert removals in the countries of interest has been estimated from:

- 1. The number of pharmacy-level Levosert sales per country and per year from product launch in 2014 until the last full year of product sales which is 2020 (IMS pharmacy sales database, 2021).
- 2. LNG-IUS user retention after 1 to 5 years of usage as reported by a post-marketing study: 0.94, 0.87, 0.82, 0.76, 0.65, respectively (Backman et al., 2001). For years outside the reported years, 0% retention is assumed resulting in a conservative estimate.

Table 2. Levosert Removals Sin	ce Proc	luct Lau	nch, Es	stimatio	n
Country	2020	2019	2018	2017	- 2

	Country	2020	2019	2018	2017	2016	2015	2014	Total
Czech	Sold	5,803	5,320	5,206	4,233	4,326	2,768	99	27,755
Republic	Removed since (estimated)	348	692	937	1,016	1,514	2,768	99	7,374
	Sold	8,736	11,765	8,971	9,282	8,619	7,931	40	55,344
Poland	Removed since (estimated)	524	1,529	1,615	2,228	3,017	7,931	40	16,884
	Sold	690	907	805	794	907	323	0	4,426
Serbia	Removed since (estimated)	41	118	145	191	317	323	0	1,135
	Sold	1,771	1,824	1,733	1,469	1,485	549	3	8,834
Slovakia	Removed since (estimated)	106	237	312	353	520	549	3	2,080
τ	Jser retention (estimated)	94%1	87%²	82%2	76%²	65%²	0%	0%	

The number of practicing OB-GYNs per country has been estimated based on data from multiple sources (WHO 2021, LKCR 2022, NIL 2021)

Distribution by indications has been estimated based on a multinational LNG-IUS patient survey, which showed that 55% of removals were in patients where IUS was prescribed for heavy menstrual bleeding and the remaining 45% for contraception (Römer et al., 2009).

A summary of Levosert sales and removals from product launch until 2020 in the four study countries, the geographical distribution of OB-GYNs, the expected achievable sample of OB-

-

¹ Based on epidemiological survey of 23,885 LNG-IUS users (Backman et al., 2001).

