# of total patients / month	

- **Q2.** Approximately, how many of your patients are **currently using** one of the following types of contraception by indication?
 - ✓ Oral/pill
 - ✓ Intrauterine device (IUD)
 - ✓ Intrauterine system (IUS)
 - ✓ Hormonal ring
 - ✓ Implant
 - ✓ Injection

	Contraception only	Heavy menstrual bleeding (with and without intended contraception)
# of patients currently using any of the above treatment types	#	#

Q3. Considering **all your patients by indication,** approximately what percentage are currently using the different types of contraception listed below?

	Contraception only	Heavy menstrual bleeding (with and without intended contraception)
Oral/pill	%	%
Intrauterine device (IUD)	%	%
Intrauterine system (IUS)	%	%
Hormonal ring	%	%
Implant	%	%
Injection	%	%
Total	100%	100%

Q4. Considering all your patients currently using intrauterine systems (IUSs) by indication, approximately what percentage are using Levosert (levonorgestrel)?

	Contraception only	Heavy menstrual bleeding (with and without intended contraception)
Proportion of patients currently using IUSs who receive Levosert	%	%

Q5. Considering **all** your patients ever having used and/or currently using **Levosert (levonorgestrel)**, what is the age distribution at the time of prescription, by indication?

	Contraception only	Heavy menstrual bleeding (with and without intended contraception)
16-24 years of age	%	%
25-34 years of age	%	%
35-44 years of age	%	%
45-54 years of age	%	%
55+ years of age	%	%
Total	100%	100%

Q6. When using **Levosert (levonorgestrel)** for **heavy menstrual bleeding (with and without intended contraception)**, what is the average time from insertion to achieving treatment effectiveness (defined as significant reduction in menstrual blood loss)?

1	Less than one month	
2	One to less than two months	
3	Two to less than three months	
4	Three to less than four months	
5	Four months or more	

Q7. In your experience, approximately what percentage of patients using **Levosert (levonorgestrel)** for the following indications need to get it **removed (with or without replacement)** by the end of each year (cumulatively since insertion)?

Please note your responses must be cumulative over time (since insertion).

	Contraception only	Heavy menstrual bleeding (with and without intended contraception)
By the end of Year 1	%	%
By the end of Year 2	%	%
By the end of Year 3	%	%
By the end of Year 4	%	%
By the end of Year 5	%	%

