By the end of Year 6	%	%

VALIDATION MESSAGE REQUIRING TRANSLATION:

ERROR: Please note your responses for each column must be cumulative. For example, your response for the end of year 2 must be equal to or greater than your response for the end of year 1, etc.

Q8. For patients who use **Levosert (levonorgestrel)** for **contraception only** for more than six years, for approximately how many years in total do these patients typically use **Levosert (levonorgestrel)**?

Please feel free to provide a fractional number of years.

	# of years	RANGE 7-10
--	------------	------------

Q9. For patients who use **Levosert** (**levonorgestrel**) for **heavy menstrual bleeding** (with and without **intended contraception**) for more than six years, for approximately how many years in total do these patients typically use **Levosert** (**levonorgestrel**)?

Please feel free to provide a fractional number of years.

	# of years	RANGE 7-10
--	------------	------------

13-02-2023

Q10. Among your patients using Levosert (levonorgestrel) for heavy menstrual bleeding (with and without intended contraception), what percentage would continue to show treatment effectiveness by the end of each year (cumulatively since insertion), while continuing to use the same Levosert (levonorgestrel) device.

Please note your responses must be cumulative over time since insertion.

Treatment effectiveness is defined as significant reduction in menstrual blood loss.

		Heavy menstrual bleeding (with and without intended contraception)
1	By the end of Year 1	%
2	By the end of Year 2	%
3	By the end of Year 3	%
4	By the end of Year 4	%
5	By the end of Year 5	%
6	By the end of Year 6	%
7	Beyond 6 years	%

VALIDATION MESSAGE REQUIRING TRANSLATION:

ERROR: Please note your responses for each column must be cumulative. For example, your response for the end of year 2 must be equal to or less than your response for the end of year 1, etc.

Q11. Considering **all** your patients ever having used and/or currently using **Levosert (levonorgestrel)** for the following indications and who had it removed (with or without replacement), approximately what percentage of these patients had **Levosert (levonorgestrel)** removed for each of the following reasons?

	Contraception only	Heavy menstrual bleeding (with and without intended contraception)
Removed per Schedule (IUS Expiry)	%	%
Planning for family	%	%
Side effects	%	%
Lack of effectiveness	%	%
Menopausal	%	%
Other (specify)	%	%
Total	100%	100%

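### Section 10.1 and Q7 do not say whether an expelled device counts as removed; if it is left out, an early loss can be scored as 7 to 10 years of use

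*Protocol*

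**What the plan says.** Protocol Section 10.1 defines the primary quantity in one sentence: "Duration of Levosert usage is defined as the difference in time between removal (with or without replacement) and insertion of the device". No other end of use is named. The expected duration is then a weighted sum. Removal in Year i, for i from 1 to 6, carries weight i, and a last term adds "likelihood of Levosert removal beyond Year 6 x total expected usage duration in those patients".

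The inputs come from Appendix 3:

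- **Q7** asks what percentage of patients using the device "need to get it removed (with or without replacement) by the end of each year (cumulatively since insertion". Its last row is "By the end of Year 6". There is no later row and no forced total of 100%.
- **Q8 and Q9** ask for the total duration in patients who use the device for more than six years. They accept only answers from 7 to 10 years.
- **Q11** asks for reasons, but only in patients who had the device removed. The list runs from scheduled expiry through family planning, side effects, lack of effectiveness and menopause to a free-text Other row.

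Expulsion is not mentioned in any of these places, nor elsewhere in the protocol text available for review. Section 10.1 also does not say how the likelihood of removal beyond Year 6 is obtained from the questionnaire.

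**The concern.** A device that has been expelled has stopped being used, but it no longer needs to be taken out. A prescriber who reads Q7 literally will leave it out of the cumulative percentages. Whatever is not reported as removed by Year 6 is then the natural candidate for the beyond-Year-6 term, where the smallest admissible weight is 7. A use that ended in the first year would enter the mean as one of at least seven years.

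This touches the primary endpoint. Sections 5.1 and 5.2 explain that the study was committed to because data are lacking to support a longer recommended duration in heavy menstrual bleeding, and Section 12.6 says that the report goes to the requesting authority. Under the reading just described, the error lengthens apparent use, which is the direction that would favour the extension.

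Analysis cannot put it right afterwards. Each prescriber answers once (Section 7.1) and no patient-level data are collected (Sections 8.3 and 9.1), so expulsions missed in Q7 cannot be recovered.

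**Working it through.** **The plan's own figures.** The protocol states no expected duration and no expulsion rate, so only its removal counts can be reproduced. Section 10.2 expects that "a sample of approximately 380 HCPs would achieve collective experience with the removal of approximately 820 Levosert IUS". Table 3 builds this by country as sample × removals ÷ OB-GYNs: 80 × 7,400/2,600 = 227.7; 150 × 16,900/5,900 = 429.7; 100 × 1,100/1,600 = 68.8; 50 × 2,100/1,100 = 95.5. The sum is 821.6 before the parts are rounded (stated: 821), and 55% of it is 451.9 (stated: 452). The Table 2 removals also reproduce exactly as units sold × (1 − retention): 7,374, 16,884, 1,135 and 2,080. In that table all loss of retention is labelled as removed.

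**The formula under the remainder rule.** Let c_i be the cumulative Q7 share by the end of Year i (c_0 = 0) and T the Q8/Q9 answer, from 7 to 10. Then

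E = Σ i × (c_i − c_(i−1)) for i = 1 to 6, + (1 − c_6) × T.

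Suppose a share e of devices is expelled in Year k and left out of Q7. Each is scored T. By the formula's own convention it should be scored k. The mean is too high by e × (T − k).

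**Size.** The expulsion share is an assumption, shown from 1% to 10%. Overstatement in years, for T = 7 to T = 10:

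| Year of loss | e = 1% | e = 3% | e = 5% | e = 10% |
|---|---|---|---|---|
| 1 | 0.06–0.09 | 0.18–0.27 | 0.30–0.45 | 0.60–0.90 |
| 3 | 0.04–0.07 | 0.12–0.21 | 0.20–0.35 | 0.40–0.70 |
| 6 | 0.01–0.04 | 0.03–0.12 | 0.05–0.20 | 0.10–0.40 |

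Every entry becomes 0 if respondents already count expulsion as removal.

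**Worked example.** Appendix 1 gives "LNG-IUS user retention after 1 to 5 years of usage as reported by a post-marketing study: 0.94, 0.87, 0.82, 0.76, 0.65, respectively", so c_1 to c_5 are 0.06, 0.13, 0.18, 0.24 and 0.35. Assume c_6 = 0.65, T = 7, and e = 5% lost in Year 1.

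- Years 1 to 6 contribute 1 × 0.06 + 2 × 0.07 + 3 × 0.05 + 4 × 0.06 + 5 × 0.11 + 6 × 0.30 = 2.94.
- Expulsions omitted, remainder rule: 2.94 + 0.35 × 7 = **5.39** years.
- Expulsions counted in Year 1: 2.94 + 0.05 × 1 + 0.30 × 7 = **5.09** years. The difference is 0.30 = 0.05 × (7 − 1).

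**Two other readings.**

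- *Expelled devices left out of the denominator as well.* E then describes only devices that were not expelled, and the gap to a mean over all insertions is e × (E − 1) for Year 1 losses. With E = 5.39 this is 0.05 × 4.39 = 0.22. With T = 10, E = 2.94 + 0.35 × 10 = 6.44 and the gap is 0.05 × 5.44 = 0.27. These compare with 0.30 and 0.45 under the remainder mechanism.
- *Unreported share dropped from the sum.* An expelled device then contributes 0 years: 2.94 + 0.30 × 7 = 5.04 against 5.09. The bias is downward, by 0.05.

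**The case against.** The strongest reply is that the protocol is silent and does not exclude expulsion. Its one worked use of the word is broad, since Table 2 turns every loss of retention into a removal. A prescriber who replaces a lost device, or takes out a displaced one, may well report it in Q7, and the error is then nil. Q11 also has a free-text Other row where such a respondent could record it. This stands, and it makes the bias conditional. It does not close the gap: respondents answer Q7 without any definition beside it, the literal wording points the other way, and the Q11 lead-in limits that item to removals. A mix of interpretations across 380 respondents would itself be a measurement fault.

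A second reply is that the remainder rule is inferred, and that its derivation may sit in an analysis plan that is not at hand. This also stands. The rule is the only one for which the questionnaire supplies data and the one that makes the likelihoods sum to 1, but Section 10.1 does not write it down. The alternatives shrink the error or reverse it.

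A third reply is that the size has no anchor in the documents and that placing all losses in Year 1 is the least favourable timing. Both are correct, which is why later years and the zero case are shown.

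**Conclusion.** The point holds as a conditional one. Section 10.1 and Q7 leave the status of expulsion open, and Q7 read literally omits it. If respondents omit it and the last likelihood is 100% minus the Year 6 figure, each device lost in Year 1 is scored 6 to 9 years too long. The mean then rises by 0.06 to 0.09 years per 1% lost in that year, and by less for later losses. The expulsion share is assumed, because the protocol gives none.

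A reader might infer that the primary endpoint is shown to be biased upward. The documents do not support that: the error is zero if respondents count expulsions, smaller if they drop those patients from the denominator, and reversed if the unreported share is dropped from the formula. Nor do they support a difference in this effect between the two indications, since no expulsion rate is given for either.

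The fault lies in a question asked once, so it is worth correcting before fielding even though its size is unknown. It is a cheap improvement.

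**What to change.** Four changes before fielding:

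1. In Section 10.1, define end of use as removal (with or without replacement) or expulsion.
2. In Q7, ask for the cumulative percentage of patients whose device was removed (with or without replacement) or expelled.
3. In Q11, add an *Expelled* row and widen the lead-in to patients who stopped using the device.
4. In Section 10.1, state that the likelihood beyond Year 6 is 100% minus the Year 6 cumulative figure from Q7.

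Respondents face one more row in Q11. Under Section 11.2, the amended protocol and questionnaire need ethics committee approval in each of the four countries before use, and the changed items must be re-translated into the four survey languages (Section 7.2).

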10.2 Determination of Sample Size

A convenience sampling approach was chosen aiming to reach a sufficiently large group of eligible HCPs who have collectively treated a substantial number of patients with Levosert for the HMB indication.

Based on the size and composition of the physician panel in the four study countries, it is estimated that a sample of approximately 380 HCPs would qualify to complete the questionnaire. Assuming an estimated 27,500 Levosert removals (from product launch until 2020) by approximately 11,200 OB-GYNs across the study countries (average 2.46 Levosert removals per OB-GYN), a sample of approximately 380 HCPs would achieve collective experience with the removal of approximately 820 Levosert IUS. Assuming an approximately balanced distribution by both indications – i.e., contraception only vs. HMB with and without intended contraception: 45% and 55%, respectively (Römer et al., 2009) –, this sample would cover approximately 450 Levosert removals in patients with HMB. Coverage of such a level of collective experience is deemed sufficient to generate a robust estimate on the expected duration of Levosert usage.

See Appendix 1 for detailed data supporting this convenience sampling approach.

10.3 Data Analysis

All analyses will be descriptive in nature. Categorical variables will be summarized using counts and percentages. Continuous variables will be summarized using the number of observations (n), mean, standard deviation (SD), median, minimum, and maximum, interquartile ranges (IQR), and 95% confidence intervals (CI), as appropriate. In addition, utilization patterns of Levosert will be visualized using plots or similar techniques.

1. Geographical distribution of Prescribers (by country)

- 2. Count and percentage of Prescribers by ranges of their professional time spent on direct patient care
- 3. Count and percentage of Prescribers by duration of their medical practice
- 4. Count and percentage of Prescribers by practice setting
- 5. Count and percentage of Prescribers having prescribed each brand of levonorgestrel IUS
- 6. Count and percentage of Prescribers having experience removing each brand of levonorgestrel (with or without replacement)
- 7. Descriptive statistics on Prescribers' count of IUS prescriptions in the past 10 years
- 8. Descriptive statistics on Prescribers' count of Levosert prescriptions and removals (with or without replacement), by indication
- 9. Descriptive statistics on Prescribers' count of patients they personally manage in a typical month without COVID-19 restrictions
- 10. Descriptive statistics on percentage of Prescribers' patients by type of contraception, by indication
- 11. Descriptive statistics on percentage of Prescribers' patients using IUSs who are receiving Levosert, by indication
- 12. Distribution of Prescriber's patients at the time of Levosert prescription among age categories, by indication
- 13. Count and percentage of Prescribers among categories of duration-of-effectiveness of Levosert for heavy menstrual bleeding
- 14. Percentage of Prescribers' patients getting Levosert removed by the end of each year, by indication
- 15. Descriptive statistics on the total duration of use of Levosert in patients who use Levosert for more than six years, by indication
- 16. Percentage of Prescribers' patients who use Levosert for heavy menstrual bleeding indication who would continue to show treatment effectiveness by the end of each year
- 17. Distribution of Prescribers' patients among reason-for-removal categories, by indication
- 18. Count and percentage of Prescribers by overall level of satisfaction with Levosert in patients who use it for three or more years, by indication
- 19. Count and percentage of Prescribers by their knowledge of the recommended duration of use of Levosert for heavy menstrual bleeding

10.4 Analysis of Subgroups

The planned subgroup analyses are summarized in Table 1.

Table 1. Key Subgroups for Analysis

Factor	Factor Classification	Subgroups to be Analysed		
Prescribing Indication	Binary	HMB with and without intended		
		contraception		
		Contraception only		
Prescriber Country	Categorical	Czech Republic		
		Poland		
		Serbia		
		Slovakia		

Where relevant, data will be further analysed by duration of Prescriber's medical practice, practice setting, number of Levosert prescriptions (by prespecified ranges), and number of Levosert removals (by prespecified ranges).

To simplify descriptive comparisons, subgroup analyses will be graphically displayed by means of forest plots, where relevant.

11 ETHICAL AND REGULATORY OBLIGATIONS

11.1 Compliance with Laws and Regulations

This DUS will be conducted in compliance with the protocol (and any potential amendments), the Declaration of Helsinki, relevant International Council for Harmonisation (ICH) guidelines, and all applicable laws and regulations of the countries in which the survey will be performed.

11.2 Ethics Committee (EC)

Conduct of the study must be approved by an appropriately constituted EC in each country. Approval is required for the study protocol, any potential protocol amendments, recruitment material (i.e., screener) and participant facing material (i.e., questionnaire) before any Prescriber can be enrolled in the DUS. Any amendment to any of these documents will require review and approval by the applicable EC in each country before the changes are implemented.

11.3 HCP Informed Consent

Prescribers will be approached through their participation in a large physician panel that is active in the study countries. Participants in this panel have already pre-consented to be approached for survey activities and do not need to be consented specifically for this study.

Screening criteria will ensure that eligible Prescribers are selected (see Section 8.1). Eligible Prescribers will be informed that their participation is voluntary, but remunerated, and that they may withdraw at any time. Premature termination of the survey will lead to waiver of the remuneration.

12 ADMINISTRATIVE REQUIREMENTS

The approved protocol shall be conducted as described; any significant protocol deviation must be documented.

12.1 Protocol Deviation/Violation

A protocol deviation/violation is any noncompliance with the DUS design. The noncompliance may be either on the part of a participating Prescriber or the survey administrator (i.e., Study Coordinating Centre). As the result of any deviation/violation, a corrective action will be developed by the survey administrator and implemented promptly. All protocol deviations/violations will be documented using the protocol deviations form and submitted to the competent EC according to their reporting guidelines.

